4. Complete physical examinations require the patient to be at the site, and will include, at a minimum, assessments of the Cardiovascular, Respiratory, Gastrointestinal and Neurological systems. Targeted physical examinations or assessments will include careful skin examination for GVHD, and other aspects as clinically indicated.
5. Height and weight will be measured at screening; only weight will be measured at other specified later visits. For home visits, stated weight may be used.
6. Includes body temperature, blood pressure, heart rate, and respiration rate and will be measured after resting for 5 minutes. For visits with infusions, vital signs will be measured within 30 minutes prior to infusion, at the end of the infusion, and at 15, 30, 45, and 60 minutes after the end of the infusion. A ±5 minute window will be permitted for all vital sign assessments.
7. Performed within 1 hour after study treatment administration and at the end of study or early termination visit. ECGs will be obtained with the patient in a semi-supine position after a 5-minute rest.
8. The HLA type of the patient and their donor kidney will be obtained from the medical record.
9. CBC must include differential and LFTs must include alkaline phosphatase, bilirubin, AST, and ALT. Urinalysis must be performed.
10. Viral loads of BKV in plasma will be measured. The results of analyses from screening must be available at the time of randomization. Results of central laboratory testing for viral load will be used for the purpose of determining eligibility/inclusion. Additional post-infusion samples may be collected, as clinically indicated. AdV, CMV, JCV, EBV, and HHV-6 viral loads will also be assessed. A whole blood or plasma BK viral load from the local laboratory may be used for the patient to qualify for screening if obtained ≤90 days before the start of screening and with any positive BK viral load (may be reported as either copies/mL or IU/mL).
11. Viral DNA isolated from blood samples will be stored for potential future sequencing/genotyping from the samples collected at baseline for viral load determination. Viral sequencing/genotyping will also potentially be performed in the event of viral recurrence and this sequencing result be compared with the baseline results.
12. Urine samples will be obtained and will be stored for urinary polyomavirus haufen testing.
13. A serum pregnancy test will be performed at screening for all patients of childbearing potential.

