
 To assess the incidence of recrudescence or new infections with target viruses (including cytomegalovirus [CMV]), but principally BKV 	
 Incidence of new target viral infections or recrudescence infections (ie, BKV, CMV, EBV, AdV, JCV, and/or HHV-6) as defined by onset of viremia and/or the presence of associated symptoms relative to baseline. Length of BKV remission (ie, time from clearance of BK viremia to reappearance of BK viremia [plasma viral load >156 copies/mL × 2 measures that are at least 2 weeks apart] or end of study)

• To determine whether patients with initially low BK viral load (ie, <10,000 copies/mL) can be prevented from developing viremia \geq10,000 copies/mL that leads to new or increased immunosuppression reduction• To determine whether patients with initially low BK viral load (ie, <10,000 copies/mL) in the investigational arm(s) develop lower viral loads than the placebo arm	
• Number of patients with screening BK viremia <10,000 copies/mL who develop BK viremia \geq10,000 copies/mL (sustained or non-sustained) or who experience a medically significant event that leads to changes in immunosuppression reduction• The absolute viral load in patients in the investigational arms versus that in patients in the placebo arm with screening BK viremia <10,000 copies/mL.
--	---

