10.7 Appendix 7: Modification of Immunosuppression

NOTE: *Viral load determinations that would lead to changes in immunosuppression (red boxes) should be repeated immediately upon receipt to confirm that action should be taken as indicated.

- a If MMF has already been reduced or discontinued more than 28 days prior, proceed to the next step in the algorithm. Other variations from the algorithm require consultation with, and approval by, the Sponsor's Medical Monitor.
- b Triple Immunosuppression: low-dose oral steroids, MMF, and calcineurin inhibitor.
- c Double Immunosuppression: MMF and calcineurin inhibitor.

Abbreviations: AST = American Society of Transplantation; KDIGO = Kidney Disease: Improving Global Outcomes; MMF = mycophenolate mofetil; PCR = polymerase chain reaction; PI = Principal Investigator (ie, Investigator); Q = very; VL = viral load

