2.3.3 Exploratory Efficacy Endpoints

The exploratory efficacy endpoints include comparison between results in patients receiving PSL versus placebo for the following:

- Change in eGFR by Modified Dose in Renal Disease (MDRD) formula.
- Changes from baseline in levels of donor-specific anti-HLA antibodies.

- Proportion of patients with resolution of BK viremia at 8 weeks post virus-specific T cell infusion.
- Proportion of patients with eGFR >20 mL/min at 24 weeks.
- Incidence of new target viral infections or recrudescent infections (i.e., BKV, CMV, EBV, AdV, JCV, and/or HHV-6) as defined by onset of viremia and/or the presence of associated symptoms relative to baseline.
- Length of BKV remission (i.e., time from clearance of BK viremia to reappearance of BK viremia (plasma viral load >156 copies/mL \times 2 measures that are at least 2 weeks apart) or end of study).
- Number of patients with screening BK viremia < 10,000 copies/mL who develop BK viremia \geq 10,000 copies/mL (sustained or non-sustained) or who experience a medically significant event that leads to changes in immunosuppression reduction.
- The absolute viral load in patients in the investigational arms versus that in patients in the placebo arm with screening BK viremia <10,000 copies/mL.

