3.1.2 Analysis Visits

Subject visits might not occur on protocol-specified days. Therefore, for the purpose of analysis, all scheduled, unscheduled, and early termination visits will be assigned to analysis visits according to the analysis windows ([Appendix 1](#)) based on study days. If there is more than 1 assessment in an analysis window, the assessment closest to the target day will be used in the analysis. If there are 2 assessments in a window equidistant from the target day, the later assessment will be used in the analysis.

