3.4.2 Exploratory Efficacy Endpoints

Observed results, change from Baseline, and percent change from baseline for eGFR estimated by MDRD and creatinine will be summarized by visit using descriptive statistics.

Donor specific anti-HLA antibodies (DSA) (yes/no) will be summarized by visit using descriptive statistics.

Resolution of viremia will be generally defined as achieving a post-baseline viral load measure below the lower limit of quantification (<LLOQ) for that viral assay. The number of patients with resolution for each virus (BKV, CMV, EBV, AdV, JCV, and/or HHV-6) will be summarized by visit and at any visits. In addition, the proportion of patients reaching at least 1 log10 reduction or <LLOQ in BK viral load post infusion will be summarized by visit and at any visits.

LLOQ values for the viruses of interest are:

BKV Viral Load (Copy/mL): LLOQ = 156

Non-BK Target Viruses:

ADV Viral Load (Copy/mL): LLOQ = 32

CMV Viral Load (Copy/mL): LLOQ = 65.6

EBV Viral Load (Copy/mL): LLOQ = 37

HHV-6 Human Herpesvirus 6 (Copy/mL): LLOQ = 110

JCV JC Virus (IU/mL): LLOQ = 76

Time-to-event endpoints will be summarized using the Kaplan-Meier method. Number of patients with events and number of patients censored and reason of censoring will be presented along with estimate for the median time (days) and its 95% CI. Time-to-event will be presented using Kaplan-Meier plots.

Time to resolution of BK viremia will be calculated as starting at randomization for patients with detectable virus and ending at the first undetectable viral load (i.e., <LLOQ). Patients who discontinued from the study early or deceased before they are observed to have achieved resolution will be censored at the last assessment date for this endpoint.

For patients who reach the resolution of BK viremia, time to reappearance of BK viremia (duration of viral remission) will be calculated as starting at the first assessment with undetectable viral load and ending at the first detectable viral load (confirmed with 2 consecutive measures at least 8 days apart, or end of study if only one measure is available). Patients not demonstrating the reappearance of viremia would be censored on the date of the latest assessment for this endpoint. Patients who discontinued from the study early or deceased before they are observed to have will be censored at the last assessment date for this endpoint.

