Time to resolution of non-BK target viral infections (i.e., associated signs, symptoms, and presence/absence of CMV, HHV-6, EBV, JCV, and/or AdV viremia) will not be performed due to limited number of events for each virus. The time to death will not be performed but the deaths will be summarized and listed.

To evaluate the impact of missing data at some timepoints, a sensitivity analysis will also be performed on BK viremia using last observation carried forward imputation.

In addition, the number and percentage for patients will be presented for following endpoints by visit unless otherwise stated.

- Patients with eGFR >20 mL/min/1.73m² at 24 weeks
- Patients with incidence of new target viral infections or recrudescent infections (i.e., BKV, CMV, EBV, AdV, JCV, and/or HHV-6) as defined by onset of viremia.
The associated symptoms are not collected so will not be considered.
- Patients with screening BK viremia <10,000 copies/mL who develop BK viremia \geq 10,000 copies/mL (sustained or non-sustained) or who experience reduction of immunosuppression which is defined as a reduction of 50% or greater of the current dose when compared to the dose at Baseline for the following medications: tacrolimus, Prograf, Envarsus, cyclosporine, Neoral Sandimmune, everolimus, sirolimus, Rapamune, rapamycin, mycophenolate mofetil, mycophenolate sodium, mycophenolic acid, Cell Cept, Myfortic, azathioprine).
 - The following drugs would not be considered for immunosuppression reduction: Prednisone, methylprednisolone, glucocorticoids, Leflunomide, Arava, Gammagard or IVIG.

Two sets of figures will be produced for mean+/- SD for change from baseline for eGFR for (Arm 1, Arm 2 and Arm 3) and (Arm 1+2 and Arm 3).

Two sets of figures will be produced for mean+/- SD for change from baseline for Creatinine for (Arm 1, Arm 2 and Arm 3) and (Arm 1+2 and Arm 3).

Listings will be provided for viral loads, eGFR, creatinine, HLA related information and donor specific anti-HLA antibodies.

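### SAP 3.4.2 specifies only by-visit counts for progression to 10,000 copies/mL or more (or immunosuppression reduction) and for new infection, not the number of patients who ever have the event

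*SAP*

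**What the plan says.** Protocol Section 3 defines the progression endpoint as a count of patients: "Number of patients with screening BK viremia <10,000 copies/mL who develop BK viremia" of 10,000 copies/mL or more. SAP 2.3.3 repeats it and makes clear that one transient crossing is enough: "sustained or non-sustained) or who experience a medically significant event that leads to changes in immunosuppression reduction". The matching objective (Protocol Section 3, SAP 2.1.3) is whether such patients can be kept from reaching that level.

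SAP 3.4.2 sets the reporting unit for this endpoint and for new or recrudescent infection: "In addition, the number and percentage for patients will be presented for following endpoints by visit unless otherwise stated". Neither bullet states otherwise; only the eGFR bullet names a time point. Earlier in the same section, resolution of viremia and the 1 log10 reduction "will be summarized by visit and at any visits".

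SAP 3.1.2 governs which value stands for a visit. First, "all scheduled, unscheduled, and early termination visits will be assigned to analysis visits". Then: "If there is more than 1 assessment in an analysis window, the assessment closest to the target day will be used in the analysis". Ties go to the later sample.

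Extra samples are expected. Footnote 10 of the Schedule of Activities (Protocol 1.3) says "Additional post-infusion samples may be collected, as clinically indicated", and Protocol Appendix 7 says that viral loads that would change immunosuppression "should be repeated immediately upon receipt to confirm that action should be taken as indicated".

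**The concern.** The endpoint asks whether a patient ever had the event; the specified table says how many patients are positive in each window. A short excursion appears in one column at most, and the columns do not show whether the same patient or different patients are positive. The favourable BK outcomes in the section get an any-visit count, while these unfavourable ones do not.

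The window rule adds a second problem for the viral-load events. It picks the value nearest a calendar target, which is reasonable for a mean by visit, but takes no account of whether the discarded value was the event. At stake is whether the table can answer its own objective of preventing progression in patients with low initial load.

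**Working it through.** The documents give no event rate, sample size or power for these endpoints, so there is no stated figure to reproduce. Three checks apply.

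**1. What by-visit counts say about the ever-count.**

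Inputs: 20 patients per arm (Protocol 9.2, SAP 2.2.3); 12 post-baseline BK windows, Weeks 2 to 24 (SAP Appendix B, Table 2); 6 non-BK windows (Appendix B, Table 4).

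Bounds: largest single-visit count ≤ patients ever positive ≤ min(n, sum of the by-visit counts).

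Suppose each column shows 1 of 20 (5%):
- BK, 12 windows: lower bound 1; upper bound min(20, 12 × 1) = 12. The ever-count lies between 1/20 = 5% and 12/20 = 60%.
- A non-BK virus, 6 windows: lower bound 1; upper bound min(20, 6 × 1) = 6. The range is 5% to 6/20 = 30%.

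The one-per-column pattern is an assumption chosen to show the range. For progression, n is the subset screened below 10,000 copies/mL, which is smaller than 20 and not stated.

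**2. Whether the window rule can drop a crossing.**

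Inputs: the Week 6 BK window is Days 37 to 50, target 43 (Appendix B, Table 2); the visit may fall on Day 43 ± 3, so Days 40 to 46 (Protocol 1.3).

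- *Scheduled crossing lost.* Visit on Day 40 reads 12,000; a repeat on Day 44 reads 9,000. Distances are |40 − 43| = 3 and |44 − 43| = 1. Day 44 is kept and the crossing leaves the table. With the visit on Day 40, an extra sample on any of Days 41 to 46 replaces it (Day 46 ties and is later): 6 of the 13 other days in the window.
- *Unscheduled crossing lost.* With the visit on Day 43, a sample on any of the other 13 days is further from target and is not used.
- *Unscheduled value used.* With the visit on Day 46, an extra sample on any of Days 41 to 45 is nearer and is used: 5 of 13 days.
- *Two scheduled visits in one window.* In Period 2 the allowance is ± 7 days. A Week 16 visit at its early limit is Day 113 − 7 = 106, inside the Week 14 window (Days 93 to 106, target 99). If the Week 14 visit was on Day 99, the Day 106 value is not used.

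**3. Which endpoints the rule reaches.**

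It selects among assessments, so it reaches BK and non-BK viral loads. Immunosuppression reduction is a fall of at least 50% in current dose against Baseline (SAP 3.3.6, 3.4.2). It comes from dose records and has no window table in Appendix B. For that limb, what by visit means is simply not defined.

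**The case against.** The strongest reply is that the text leaves room for the right table. SAP Table 1 lists these endpoints as plain Yes/No, and the bullets speak of developing an event, of incidence and of onset. If each patient were shown once, at first onset, the columns would add up to the ever-count. Viral loads and dose changes are also listed by patient. This stands in part: the accurate statement is that the ever-count is not specified. It does not close the gap, because resolution is also plain Yes/No in Table 1 yet 3.4.2 still spells out the any-visit count for it, and a listing is not a prespecified summary.

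Several stronger readings are tempting, and the documents do not support them:
- *Unscheduled peaks are discarded.* Not as a class. They are assigned to windows, used when nearest the target, and remain in the listings.
- *Immunosuppression reductions are lost in the same way.* The window rule does not apply to dose records. A patient whose listed drug is cut by at least 50% meets the composite through that limb whichever sample is kept, and stays positive while the dose stays down. In the Day 40/44 example the patient is missed by the composite only without such a cut and with no other retained value at or above 10,000; the separate viral-load row in Table 1 misses the crossing either way.
- *Appendix 7 creates peaks seen only on unscheduled samples.* The repeat follows a value that has already raised the question. The thresholds are in a figure not shown, and the appendix does not say that repeats go to the central laboratory.
- *Failures vanish mainly from placebo, hiding a PSL effect.* Protocol 4.1 and 6.8 expect that fewer PSL patients may meet criteria for immunosuppression reduction, so a difference between arms is plausible. Nothing in the documents gives its size or shows that lost crossings would favour either arm.

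It is also fair that these endpoints are exploratory and summarised descriptively (Protocol 9.4.4).

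**Conclusion.** The point holds as an under-specification with a real consequence. As written, SAP 3.4.2 asks only for by-visit counts of two endpoints, and the progression endpoint is defined per patient. Those counts leave the ever-count open over a wide range (5% to 60% in the BK illustration). The closest-to-target rule, without an exception for events, can also remove a scheduled or unscheduled viral-load crossing.

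The range assumes one positive patient per window and a denominator of 20, which overstates the eligible group for progression. How often a crossing would be lost cannot be estimated from the documents, since it depends on visit timing and on how many extra samples are drawn. No sample size, power, alpha, primary safety result or key secondary viral-load result is affected.

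**What to change.** In SAP 3.4.2, add for both endpoints a per-patient row for the event at any time post-baseline, as the main row. Derive the viral-load events from all post-baseline central-laboratory results, including unscheduled and repeat samples. Count immunosuppression reduction once per patient from dose records, using the SAP's existing 50% definition. Show the size of the below-10,000 subset as the denominator for progression. Keep the by-visit rows as supportive.

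In SAP 3.1.2, state that the closest-to-target rule applies to by-visit summaries only. Without this, an any-visit row alone would still leave open which samples count.

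The cost is two sentences and one extra row per table. The downside is that patients sampled more often have more chances to cross. A scheduled-visits-only version of the row, using every scheduled result, shown beside the main one would let readers judge how much this matters.

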3 OBJECTIVES AND ENDPOINTS

Objectives	Endpoints
Primary 
 To compare the safety and tolerability of PSL to placebo in kidney transplant recipients 	
 Treatment-emergent adverse events (TEAEs) and changes in vital signs, physical exams, clinical laboratory assessments, and electrocardiograms (ECGs)
Key Secondary 
 To assess the overall efficacy of PSL to suppress plasma BK viral load compared with placebo 	
 Change in BK viremia in patients receiving PSL compared to patients receiving placebo
Other Secondary 
 To compare the relative efficacy of different dosing regimens of PSL to suppress BK viral load versus placebo 	
 Change in BK viremia in patients receiving different dosing regimens of PSL compared to patients receiving placebo
Exploratory 
 To assess change in estimated glomerular filtration rate (eGFR) over 24 weeks in recipients of PSL versus placebo 	
 Change in eGFR by Modified Dose in Renal Disease (MDRD) formula in recipients of PSL versus placebo

 To identify changes in donor-specific anti-human leukocyte antigen (anti-HLA) antibodies in recipients of PSL versus placebo 	
 Changes from baseline in levels of donor-specific anti-HLA antibodies in recipients of PSL versus placebo

 To determine the proportion of patients with resolution of BK viremia at 8 weeks post virus-specific T cell infusion 	
 Proportion of patients with resolution of BK viremia at 8 weeks post - Virus-Specific T cell infusion

 To assess kidney allograft survival at 24 weeks 	
 Proportion of patients with eGFR >20 mL/min at 24 weeks

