3.1.5 Handling of Dropouts and Missing Data

In general, data will be analyzed and presented as observed and will not be imputed for the analysis of efficacy and safety, unless otherwise specified.

In case the start and end dates for adverse events and concomitant medications/procedures are missing or incomplete, the missing component(s) will be assumed as the most conservative value possible. For example, AEs with missing start dates, but with stop dates either overlapping into the treatment period or missing, will be counted as treatment-emergent, taking the worst-case approach. When partial dates are present in the data, both a partial start date and/or a partial stop date will be evaluated to determine whether it can be conclusively established that the AE started prior to the start of study treatment or ended prior to the start of study treatment. If the above cannot be conclusively established based on the partial and/or present dates, then the AE will be considered as treatment-emergent. Actual data values as they appear in the original case report forms (CRFs) will be presented in the data listings.

Viral load values below the limit of quantification will be imputed as the limit of quantification minus 0.1 unit (for CMV) or minus 1 unit (for other viruses).

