3.4.3 Other Endpoints

Observed results, change from baseline, and percent change from baseline for eGFR (estimated by the creatinine-cystatin C method) will be summarized by visit using descriptive statistics. The number of days of hospitalizations and re-hospitalizations for any reason will be summarized.

Number and percentage for patients will be presented for following endpoints.

- Patients with biopsy-proven acute allograft rejection. The results will be provided by severity (adjudicated Banff classification)
- Patients using immunosuppressive agents, including specific immunosuppressive agents used. The doses, and any changes in dose will be listed.
- Patients with kidney injury requiring hemodialysis
- Patients with hospitalizations/re-hospitalizations for any reason

The use of antiviral therapies will be listed as concomitant medications but not summarized.

The analyses for all the efficacy endpoints are summarized in Table 1:

Table 1: Efficacy Endpoints Summary and Statistical Analysis

| Type of Endpoint | Summary Table | |
|---|------------------------|---------------------|
| | Population | Variables[*]/Method |
| Continuous | | |
| • BK viral load | Observed/Chg/Pchg | |
| • eGFR by MDRD | Observed/Chg/Pchg | |
| • eGFR by Creatinine-cystatin C | Observed/Chg/Pchg | |
| Time to event [#] | | |
| • Time to BKV resolution | Kaplan-Meier | |
| • Duration of BKV remission | Kaplan-Meier | |
| Category | | |
| • BKV resolution | Categories: Yes/No | |
| • 1 Log10 reduction of BK viral post infusion | Categories: Yes/No | |
| • Patients with screening BK viremia <10,000 copies/mL develop BK viremia ≥10,000 copies/mL | Categories: Yes/No | |
| • Donor specific anti-HLA antibodies | Categories: Yes/No | |
| • eGFR >20 mL/min/1.73m ² | Categories: Yes/No | |
| • New viral infection | Categories: Yes/No | |
| • Immunosuppression reduction | Categories: Yes/No | |
| • Immunosuppressive agents | Categories: agent type | |
| • Biopsy-proven acute allograft rejection | Categories: severity | |
| • Kidney injury requiring hemodialysis | Categories: Yes/No | |
| Category and continuous | | |
| • Hospitalizations/re-hospitalizations | Yes/No; Duration | |

N/A = Not Applicable.

[*] Chg = Change from Baseline; Pchg = Percent Change from Baseline.

[\$] Line plot will be generated.

[#] Kaplan-Meier plot will be generated for each endpoint.

[**] Ratio is defined as unique clonotype donor DNA/patient DNA*100.

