3.5.2 Clinical Laboratory Tests

Laboratory assessments comprise safety laboratory tests (hematology, clinical chemistry and urinalysis) and other laboratory tests.

Descriptive statistics will be provided for clinical laboratory test results (hematology, clinical chemistry and routine urinalysis) and changes from baseline. With the exception of the LOCF sensitivity analysis of BK viremia, missing values for any of the laboratory evaluations will not be imputed; that is, only observed case data will be used.

A shift table, presenting the 2-way frequency tabulation for baseline and the worst post-baseline value according to the NCI CTCAE grade, will be provided for clinical laboratory.

In addition, the number and percentage of patients with the following potentially clinically significant abnormal liver function tests will be summarized:

- Potential Hy's Law cases: ALT or AST $\geq 3 \times \text{ULN}$ and total bilirubin $\geq 2 \times \text{ULN}$ and Alkaline phosphatase (ALP) $< 2 \times \text{ULN}$.

Listings will be presented for all laboratory data and all test values outside the normal range will be flagged.

In addition, other laboratory tests, including pregnancy test, serology test, testing for HIV, HCV, HBV and CMV, and donor specific anti-HLA antibodies will be presented in by-patient listings.

3.5.3 *Vital Signs*

Descriptive statistics will be provided for vital signs (including blood pressures, pulse rate, respiratory rate, oximetry, and body temperature), body weights, and BMIs by treatment group at each scheduled visit. Changes from baseline will also be summarized.

All vital sign data will be listed by patient.

3.5.4 *Electrocardiograms*

ECG measurements include heart rate (bpm), measures PR (msec), QRS (msec), QT (msec), and QTc (msec) (corrected using Fridericia's and Bazett's methods). Descriptive statistics will be provided for the observed measurements and change from baseline.

All ECG parameters and the Investigator interpretation of findings including details of any abnormalities will be listed by patient.

3.5.5 *Physical Examinations*

All abnormal physical examination findings, including details of any abnormalities will be listed by patient.

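### Kidney allograft survival is measured as observed eGFR above 20 at Week 24, with no failure rule for death, graft loss or dialysis and no stated denominator

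*SAP*

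**What the plan says.** Protocol Section 3 sets an exploratory objective, "To assess kidney allograft survival at 24 weeks", and pairs it with one endpoint, "Proportion of patients with eGFR >20 mL/min at 24 weeks". SAP 3.4.2 carries this forward as a number and percentage of "Patients with eGFR >20 mL/min/1.73m² at 24 weeks". Table 1 in SAP 3.4.3 gives it only Yes and No categories.

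The missing-data rules are:

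- SAP 3.1.5, for efficacy and safety in general: "data will be analyzed and presented as observed and will not be imputed for the analysis of efficacy and safety, unless otherwise specified".
- SAP 3.5.2, for laboratory data, with LOCF for BK viremia as the only exception: "missing values for any of the laboratory evaluations will not be imputed; that is, only observed case data will be used".
- SAP 3.4.2, the only missing-data sensitivity analysis: "a sensitivity analysis will also be performed on BK viremia using last observation carried forward imputation". It does not cover eGFR.

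SAP 3.4 bases efficacy analyses on the ITT population. No section says whether the eGFR percentage is taken over all randomized patients or over those with a Week 24 value. Deaths are summarized and listed (SAP 3.4.2) and hemodialysis has its own row (SAP 3.4.3), but neither feeds into this endpoint.

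**The concern.** The objective concerns graft survival, but the measure is a laboratory threshold that needs a creatinine at Week 24. Some of the failures that a survival endpoint exists to count cannot supply one: a patient who has died has no value, and a patient who loses the graft and leaves may have none. Under an observed-case rule these patients disappear from the percentage.

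A second problem does not depend on missing data. eGFR is calculated from serum creatinine (Protocol 8.1.2), and dialysis itself removes creatinine. No rule prevents a patient on dialysis from being classed as a Yes on a value that does not describe the graft.

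Exclusion criterion 13 keeps out patients with eGFR below 20, so nearly everyone starts at or above the threshold and the result rests on a few failures. Small classification choices can then move the figure and the comparison between arms.

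**Working it through.** **No figure to reproduce.** The documents give no expected survival, death, graft-loss or dropout rate for this endpoint. All event counts below are assumptions. The group sizes are the plan's: 20 per arm, hence 40 in pooled PSL.

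**Who lacks a Week 24 value.** Patients leaving early are to have the Week 24 assessments at exit (Protocol 7.2; schedule of activities, footnote 21). SAP 3.1.2, however, assigns early-termination visits by study day. In SAP Appendix B the clinical-laboratory window for Week 20 is days 128 to 155, and Week 24 starts after day 155. I take this table to govern eGFR, since eGFR comes from creatinine and has no window table of its own. An exit sample on day 140 therefore counts as Week 20, and a patient who dies or leaves by day 155 has no Week 24 value. An exit after day 155 can still supply one.

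**Contrast within the SAP.** For time to BK resolution and for duration of remission, SAP 3.4.2 states how early discontinuation and death are handled. It has no such statement for graft survival.

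**One death by day 155, everyone else above 20:**

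- Arm of 20: 19/19 = 100% if omitted, 19/20 = 95% if counted as failure.
- Pooled PSL: 39/39 = 100% if omitted, 39/40 = 97.5% if counted.

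The same omission moves placebo by 5 points and pooled PSL by 2.5. Two omitted deaths in an arm of 20 read 18/18 = 100% instead of 18/20 = 90%.

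**One graft loss, everyone else above 20, arm of 20.** If the patient stays and measures 20 or less, the result is 19/20 = 95% with or without a failure rule. Only if the patient has no Week 24 value does it read 19/19 = 100%.

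**A mixed case: d = 1 death, g = 1 graft loss, w = 2 other early exits.** All others are observed above 20, so the Yes count is N − d − g − w: 16 of 20, or 36 of 40.

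| Handling | Formula | N = 20 | N = 40 |
|---|---|---|---|
| All three types left out | (N−d−g−w)/(N−d−g−w) | 16/16 = 100% | 36/36 = 100% |
| Graft loss measured at 20 or less; death and exits left out | (N−d−g−w)/(N−d−w) | 16/17 = 94.1% | 36/37 = 97.3% |
| Death and graft loss fail; exits left out | (N−d−g−w)/(N−w) | 16/18 = 88.9% | 36/38 = 94.7% |
| ITT denominator; nothing missing counts as Yes | (N−d−g−w)/N | 16/20 = 80.0% | 36/40 = 90.0% |
| Death and graft loss fail; exits taken as surviving | (N−d−g)/N | 18/20 = 90.0% | 38/40 = 95.0% |

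The same patients in one arm give anything from 80% to 100%.

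**Early exits alone.** Take 40 patients, 36 completers with 97% survival and 4 exits. The observed-case figure is 97%. The full-group figure is (36 × 0.97 + 4 × p)/40, where p is survival among the exits:

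- p = 0.97 gives 97.0%.
- p = 0.75 gives 94.8%.
- p = 1.00 gives 97.3%.

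Exits alone therefore do not fix the direction of the bias.

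**The case against.** A reader might infer that everyone who dies, loses the graft or leaves early drops out of the denominator, so that survival is certain to be overstated. The documents do not support that reading, for four reasons:

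- **Denominator.** Efficacy analyses are on ITT. The two missing-data rules say that values are not imputed; neither says that percentages use only non-missing patients. Over the ITT count, two exits among 20 with working grafts would read 18/20 = 90%, an understatement.
- **Graft loss.** It is not itself listed as a reason to stop treatment or leave the study (Protocol 7.1, 7.2). A patient who stays and measures 20 or less is already a No. Protocol 7.2 does allow discontinuation for a serious or clinically significant event, so exit after graft loss is plausible but not a given.
- **Early exit.** It biases upward only if those who leave do worse than those who stay, which the documents do not show.
- **Death.** Counting death as failure selects all-cause over death-censored graft survival, and the plan does not say which is meant.

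It is also fair to say that the endpoint is exploratory and descriptive (Protocol 9.4.4), and that deaths and hemodialysis are visible elsewhere in a small trial.

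These points stand, and they remove the certainty about direction. They do not remove the gap. Separate counts of deaths and dialysis do not show how many patients are alive with a working graft. An unwritten denominator leaves a choice between, for example, 18/18 and 18/20 to be made at analysis. The question of dialysis creatinine is unaffected.

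**Conclusion.** The concern holds in a limited form. The plan measures allograft survival only by an observed eGFR threshold, with no failure rule for death, graft loss or dialysis, no stated denominator and no sensitivity analysis for missing eGFR. On the observed-case reading, which is the natural one, deaths by day 155 and graft losses that leave by then are omitted. The figure then rises by about 5 points per omitted failure in an arm of 20 and about 2.5 points in pooled PSL. For deaths, this is an overstatement of all-cause survival. On an ITT denominator the error can run the other way.

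These sizes rest on assumed event counts and on all other patients being observed above 20. A definite upward bias is not established. The point merits correction because following the stated rules can give a misleading survival figure, but it bears on an exploratory result and not on the trial's main conclusions.

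**What to change.** Amend the SAP before database lock:

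1. Keep the eGFR >20 row as the protocol defines it, and state its denominator.
2. Add an allograft-survival row on all ITT patients. Count as failure graft loss or kidney injury requiring hemodialysis by Week 24, or a Week 24 eGFR of 20 or less. Dialysis then overrides any creatinine-based value. Neither document gives graft loss its own endpoint, so say which records identify it.
3. Show death as failure (all-cause), with a death-censored version alongside.
4. Show patients missing for other reasons in a separate row, with a missing-as-failure sensitivity analysis.

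The cost is SAP wording and one extra exploratory table. Deaths, hemodialysis and creatinine are already planned for reporting. The survival figure may be slightly less favourable than an observed-case percentage.
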